#### 4.5.1.4 Concomitant medication, known drug reactions and interaction with other therapies

Renal clearance of medications will be changed as a result of the participants having AKI, therefore, all drug doses should be checked by a pharmacist. Participants receiving corticosteroids, antibiotics, tetracyclines, potassium supplements and/or any medicinal products mentioned in section 4.5 of the SmPC should be closely monitored.

#### 4.5.1.5 Drug storage and supply

The study drug will come from routine hospital stock and will be sourced locally by and stored at each research site according to accredited standards for routine pharmacy practice. As this is an open trial which does not involve the use of placebo or dummy infusions, no special measures are needed in terms of packaging or supply beyond those routinely required.

#### 4.5.1.6 Preparation and labelling

IV 8.4% w/v sodium bicarbonate will be readily available on the ICU. Trial-specific labelling is not required as the IMP has a marketing authorisation in the UK, is being used within the terms of its marketing authorisation and is dispensed to a trial participant in accordance with a prescription given by an authorised healthcare professional.

#### 4.5.1.7 Summary of Product Characteristics (SmPC)

A copy of the SmPC will be filed in the Trial Master File (TMF) and Investigator Site Files (ISF).

#### 4.5.2 Control – no IV sodium bicarbonate

Participants randomised to the control group will not receive IV sodium bicarbonate.

#### 4.5.3 Co-interventions

Patients in whom a decision has already been made to initiate KRT at time of screening are not eligible to participate in this trial.

Once eligible patients have been randomised, indications to commence KRT may subsequently develop and in these situations KRT may be initiated at the discretion of the treating clinician.

As a guide, KRT can be considered where at least two of the following criteria are present:

1. urine output <0.3mL/kg/h for at least 24 hours;
2. arterial pH <7.25 despite adequate volume resuscitation or in the intervention arm an arterial pH <7.25 after adequate administration of sodium bicarbonate (defined as sodium bicarbonate treatment for 24 hours and administration of the maximum 500 ml/24 hours );
3. hyperkalaemia (serum potassium >6.5 mmol/L);
4. fluid overload intractable to diuretics.

Reasons for commencing KRT will be recorded on the CRF. In both groups, all other care will be provided by the discretion of the treating clinical team according to local routine practice.

[figure not shown]
#### 4.5.4 Monitoring adherence to interventions

In the intervention group, adherence to the protocol will be defined as receipt of IV sodium bicarbonate when pH <7.30 until critical care unit discharge or commencement of KRT. Protocol adherence in the control group will be defined by the absence of IV sodium bicarbonate.

During site set-up and recruitment, sites will receive standardised training materials, including an enhanced site training and education website that explicitly cover the current evidence base, the rationale for the study, and treatment protocols in both groups.

During the study, sites will be provided with individual site reports displaying their adherence data and highlighting areas for improvement. Protocol adherence will also be monitored as part of the central monitoring plan. Non-adherence will trigger a query to the participating site who will be required to provide justification.

## MOSAICC Intervention flow diagram

\* After randomisation, indications to commence KRT may subsequently develop and in these situations KRT may be initiated at the discretion of the treating clinician. As a guide, KRT may be considered where at least two of the following criteria are present:

1. urine output  $< 0.3$  mL/kg/h for at least 24 hours;
2. arterial pH  $< 7.25$  despite adequate volume resuscitation, or in the intervention group an arterial pH  $< 7.25$  after adequate administration of sodium bicarbonate (defined as sodium bicarbonate treatment for 24 hours and administration of the maximum 500ml/24hours, as per algorithm above);
3. hyperkalaemia (serum potassium  $> 6.5$  mmol/L);
4. fluid overload intractable to diuretics.

## **4.6 Withdrawal procedures**

### **4.6.1 Withdrawal from randomised therapy**

Any physician involved in the usual care of patients may withdraw patients from randomised treatment using their clinical judgement. This might occur due to the occurrence of an AE or the onset of symptoms that limit tolerability. All reasons for withdrawal will be noted in the participant's CRF and medical notes.

### **4.6.2 Refusal or withdrawals of consent**

If a patient declines informed deferred consent, or a legal representative advises that they believe the patient would not choose to participate in the trial, and, if a patient or their legal representative (Personal or Professional) withdraws consent at any time during the trial - this decision will be respected and will be abided by.

All data up to the point of this decision will be retained in the trial unless the patient or legal representative requests otherwise. Where possible, patients and legal representatives will be asked if they are happy for data to continue to be collected from the medical records for the trial, emphasising that this will not require any further contact with the patient/legal representative.

## **4.7 Assessment and management of risk**

The MHRA has categorised MOSAICC as: Type A = No higher than the risk of standard medical care.

This assessment is based on the fact that the risk to the participant is no greater than routine, standard medical care that they would receive if they were not enrolled into this trial. Categorisation of the risk was determined using the Marketing Authorisation of the IMP being investigated and that its use is well established in clinical practice in critical care units in the UK (see Section 4.5.1.1). The IMP under investigation is licensed in the UK.

## **4.8 Pharmacovigilance and safety reporting**

As per 4.2, participants will be critically ill and being treated in a critical care unit (defined as intensive care unit or a combined intensive care/high dependency unit) therefore general safety monitoring is as per standard of care for the setting.

### **4.8.1 Definitions**

Adverse Event (AE) reporting will follow the Health Research Authority guidelines on safety reporting for clinical trials of investigational medicinal products (CTIMPs). The following definitions have been adapted from the Medicines for Human Use (Clinical Trials) Regulations 2004 (UK), for trials with an investigational medicinal product:

#### **Adverse Event (AE)**

An untoward medical occurrence in a participant participating in a trial and/or to whom an investigational medicinal product has been administered, which is not necessarily caused by or related to that product.

#### **Adverse Reaction (AR)**

An untoward and unintended response in a participant to an investigational medicinal product which is related to any dose administered to that participant.

## Serious Adverse Event (SAE)

Any adverse event that:

- results in death;
- is life-threatening;
- requires inpatient hospitalisation or prolongation of existing hospitalisation;
- results in persistent or significant disability/incapacity; or
- is a congenital anomaly or birth defect.

“Life-threatening” refers to an event in which the subject was at risk of death at the time of the event. It does not refer to an event that hypothetically might have caused death if it were more severe.

“Hospitalisation” refers to inpatient, regardless of length of stay. This includes admission for continued observation. Any admission for pre-existing conditions that have not worsened, or elective procedures, do not constitute an SAE.

Important adverse events that are not immediately life-threatening, do not result in death or hospitalisation but may jeopardise the subject or require intervention to prevent one or any of the other outcomes listed in the definition above should also be considered as serious.

## Serious Adverse Reaction (SAR)

An adverse reaction that is classed as serious and, in the opinion of the reporting Investigator, believed with reasonable probability to be related to the treatment, based on the information in the SmPC.

## Suspected Unexpected Serious Adverse Reaction (SUSAR)

A serious adverse reaction, the nature and severity of which is not consistent with the information in the SmPC.

### 4.8.2 Assessment of AEs and SAEs

The PI, or other medically qualified investigator as listed on the Delegation Log, should make an assessment of severity, relatedness and expectedness, categorised as follows:

#### 4.8.2.1 Severity

- **None:** indicates no event or complication
- **Mild:** complications result in only temporary harm and do not require clinical treatment
- **Moderate:** complications require clinical treatment but do not result in prolongation of hospital stay. Does not usually result in permanent harm and where this does occur the harm does not cause functional limitations to the patient
- **Severe:** complications require clinical treatment and results in prolongation of hospital stay and/or permanent functional limitation
- **Life-threatening:** complications that may lead to death
- **Fatal:** where the participant died as a direct result of the complication/adverse event.

*An event assessed as 'Severe', 'Life-threatening' or 'Fatal' will be considered an SAE, SAR or SUSAR.*

#### 4.8.2.2 Relatedness

- **None:** there is no evidence of any relationship to the trial treatment
- **Unlikely:** there is little evidence to suggest a relationship to the trial treatment, and there is another reasonable explanation of the event
- **Possibly:** there is some evidence to suggest a relationship to the trial treatment, although the influence of other factors may have contributed to the event
- **Probably:** there is probable evidence to suggest a relationship to the trial treatment, and the influence of other factors is unlikely
- **Definitely:** there is clear evidence to suggest a relationship to the trial treatment, and other possible contributing factors can be ruled out.

*All AEs/SAEs judged as having a reasonable suspected causal relationship (e.g. possibly, probably, definitely) to the study drug will be considered as ARs/SARs.*

#### 4.8.2.3 Expectedness

- **Expected:** the event is consistent with the information in section 4.8 in the SmPC.
- **Unexpected:** the event is not consistent with the information in section 4.8 in the SmPC.

### 4.8.3 Recording and reporting

Occurrences of the specified, expected (S)AEs/ARs (Appendix 2) will be recorded and reported for all randomised patients from the time of randomisation until critical care unit discharge or 90 days (whichever comes first). If a participant is readmitted to the critical care unit within the 90 days, safety monitoring will be recommenced.

All other (S)ARs will be recorded and reported from the time of first dose of sodium bicarbonate until 24 hours after the final dose.

Considering that all eligible patients are critically ill and at increased risk of experiencing multiple adverse events due to the complexity and severity of their condition – occurrences of non-specified, unexpected AEs will only be reported if they are assessed to be serious (i.e. not events that are part of the natural history of the primary disease process or expected complications of critical illness).

The following event(s) will not be reported as SAEs:

- Death (Collected as a study outcome. Note that death itself should not be reported as an SAE, but the suspected cause of death should be assessed for severity, relatedness and expectedness as detailed above)
- Commencement of kidney replacement therapy (Collected as a study outcome.)
- Any events that are part of the natural history of the primary disease process or expected complications of critical illness, and unrelated to any clinical trial procedures

All SAEs (other than those defined in the protocol as not requiring reporting), SARS and SUSARs must be recorded in the patients' medical notes and reported to ICNARC CTU within 24 hours of observing or learning of the SAE/SAR/SUSAR(s). This involves completing and uploading the MOSAICC SAE Report Form to the secure electronic data entry system, and notifying ICNARC CTU of this upload by e-mailing [[contact]](mailto:[contact]). Staff should not wait until all information about the event is available before sending SAE notification. Information not available at the time of the initial report must be documented and submitted as it becomes available.

The process for recording and reporting adverse events and serious adverse events is summarised in Figure 1.

On receipt of an SAE/SAR/SUSAR report, a member of the ICNARC CTU will first evaluate the report for completeness and internal consistency. Then, a clinical member of the MOSAICC Trial Management Group (TMG) will evaluate the event for severity, relatedness and expectedness to determine whether or not the case qualifies for expedited reporting to the MHRA, REC and other competent authorities.

Fatal or life threatening SUSARs must be reported within 7 days and non-fatal and non-life threatening SUSARs within 15 days of first being aware of the SUSAR.

All other non-specified AEs that occur between randomisation and 90 days post-randomisation (or ICU discharge, if sooner) must be recorded in the participant's medical notes.

The ICNARC CTU will provide safety information to the Data Monitoring and Ethics Committee (DMEC) on a basis deemed appropriate by the DMEC.

[figure not shown]

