Secondary outcomes	
 
- Mortality at critical care unit discharge, 28 days and one year;
 
- Receipt and duration of respiratory, renal, and advanced cardiovascular organ support in critical care;
 
- Duration of critical care unit and acute hospital stay;
 
- On-going requirement for KRT at 90 days and one year
 

Economic outcomes	
Primary economic evaluation outcome:
 
 
- Incremental costs, QALYs and net monetary benefit at 90 days following randomisation (cost-effectiveness)
 
 
Secondary economic evaluation outcomes:
 
 
- Health-related quality of life at 90 days and one year;
 
- Resource use and costs at 90-days and one year; and
 
- Estimated lifetime incremental cost-effectiveness
 

Investigational Medicinal Product	Sodium bicarbonate 8.4% w/v, intravenous infusion
Formulation, Dose, Route of Administration	Starting dose is 50 ml administered over 30-60 minutes, with repeated doses depending on subsequent pH readings and clinical status (including haemodynamic monitoring heart rate, blood pressure), as well as blood gas analysis (including pCO 2 , HCO 3 and electrolytes) up to a maximum of 500 ml per 24 hours.

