## 1.2 Sodium bicarbonate

A recent randomised controlled trial (RCT) evaluating the use of sodium bicarbonate in critically ill patients with acidosis found a significant reduction in 28-day mortality (46% sodium bicarbonate vs. 63% control) and use of KRT in a pre-specified subgroup of patients with AKI (n=182). However, such sub-group analyses must be treated with caution, and the authors rightly called for a larger RCT to address this question.

While there are evidence-based recommendations for the use of sodium bicarbonate in other populations, such as for patients with chronic kidney disease (CKD) and end stage renal disease, possible side effects, such as rebound alkalosis, cardiac suppression, potential intracellular acidification due to the accumulation of carbon dioxide and risk of hypocalcaemia, have been identified.

Currently, there is uncertainty among critical care clinicians as to whether sodium bicarbonate should be used for routine treatment of acidosis in patients with AKI. A survey of UK critical care units indicated substantial variation in practice, with 23% of clinicians reporting some use of sodium bicarbonate for patients with moderate acidosis (pH 7.20–7.30), 34% for severe acidosis (pH 7.10–7.20), 21% for very severe acidosis (pH < 7.10) and 22% reporting no use at all. These results are consistent with a similar survey conducted in the US. There is currently little high-quality evidence for the use of sodium bicarbonate in patients with acidosis and AKI which is likely to lead to varied use in critical care units worldwide.

The Multicentre evaluation Of Sodium bicarbonate in Acute kidney Injury in Critical Care (MOSAICC) RCT will address the clinically important question of whether in critically ill adults with metabolic acidosis and AKI, is treatment with IV 8.4% weight by volume (w/v) sodium bicarbonate superior to no IV sodium bicarbonate in terms of all-cause mortality at 90 days (clinical effectiveness) and incremental costs, quality-adjusted life years (QALYs) and net monetary benefit at 90 days (cost-effectiveness). This evaluation will have a large and immediate impact on clinical practice and on patient outcomes in the NHS and worldwide.

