### 4.3.2 Exclusion criteria

1. Respiratory acidosis (acute or chronic)
2. Clinical decision already in place to start patient on kidney replacement therapy (KRT)
3. Deemed unsuitable for KRT
4. Acute diarrhoea, including high output stoma/ileostomy
5. Percutaneous biliary drainage
6. Documented Stage 4 chronic kidney disease (CKD) [eGFR <30ml/min/1.73m^2] or end stage kidney disease (ESKD) on dialysis
7. Known renal tubular acidosis
8. Diabetic ketoacidosis
9. High anion gap acid poisoning (e.g. polyethylene glycol (PEG), aspirin, methanol)
10. Known to be pregnant
11. Symptomatic hypocalcaemia (Ionised calcium <1.05 mmol/L) †
12. Hyponatraemia (Plasma sodium >150 mmol/L) †
13. Severe hypokalaemia (Potassium <3.0 mmol/L) †
14. Solid organ transplant
15. Death perceived as imminent
16. Known hypersensitivity to sodium bicarbonate or to any of the excipients (see section 6.1 of the SmPC)

† Exclusion criteria 11-13 are dynamic, and if corrected, patient may be reconsidered for the trial.

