#### 4.4.1.1 Blinding

MOSAICC is an open trial. With frequent blood gas measurements required as part of routine critical care practice, it is impossible to blind the effects of intravenous administration of sodium bicarbonate.

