#### 4.5.1.2 Dosage schedule

50 ml of IV 8.4% w/v sodium bicarbonate administered over 30-60 minutes. Arterial blood gas (ABG) analysis should be performed 1-2 hours after each infusion.

Participants should be assessed for response to treatment and repeated doses should be administered depending on subsequent pH readings and clinical status (including haemodynamic monitoring heart rate, blood pressure), as well as blood gas analysis (including  $p\text{CO}_2$ ,  $\text{HCO}_3^-$  and electrolytes) up to a maximum of 500 ml per 24-hour period (see *MOSAICC Intervention flow diagram*).

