### 13.2 Appendix 2 – Expected adverse events/reactions.

- Alkalosis (defined as arterial blood gas value of pH  $\geq 7.55$ )
- Hypokalaemia
- Hypernatraemia
- Hyperosmolarity
- Hypocalcaemia
- Hypoglycaemia
- Deterioration of hemodynamic status associated with volume overload
- Extravasation
- Tissue necrosis caused by incorrect administration (intra-arterial, paravenous)

If an SAE/SAR, as defined in Section 4.8, occurs this should be recorded and reported as described in Section 4.8.

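### Most listed laboratory harms have no cut-off or new-onset rule in an open trial, and two effects the protocol itself raises are missing from the list recorded in both arms

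*Protocol*

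**What the plan says.** Section 4.4.1.1 states that "MOSAICC is an open trial", so whoever identifies and classifies an event knows the allocation.

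Section 4.8.3 sets up two streams. The events in Appendix 2 are collected in all randomised patients, from randomisation to critical care discharge or 90 days. For everything else, "All other (S)ARs will be recorded and reported from the time of first dose of sodium bicarbonate until 24 hours after the final dose". Unlisted, unexpected events are reported only if serious. Complications to be expected in critical illness and unrelated to trial procedures are not reported as serious events. Remaining unlisted events go into the medical notes.

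Appendix 2 defines one laboratory event numerically. Its entry begins "Alkalosis (defined as arterial blood gas value of pH" and sets the limit at 7.55 or above. Hypokalaemia, hypernatraemia, hyperosmolarity, hypocalcaemia and hypoglycaemia stand as bare terms.

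On sampling, section 4.5.1.2 says "Arterial blood gas (ABG) analysis should be performed 1-2 hours after each infusion". The text gives no corresponding schedule for control, although section 4.4.1.1 reasons from "With frequent blood gas measurements required as part of routine critical care practice".

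On anticipated harms, section 1.2 names "possible side effects, such as rebound alkalosis, cardiac suppression, potential intracellular acidification due to the accumulation of carbon dioxide", and section 1.3 reports that bicarbonate raised PaCO2. Neither cardiac suppression nor raised PaCO2 is in Appendix 2. The closest entry is haemodynamic worsening from volume overload.

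**The concern.** Appendix 2 is the only set of events collected on the same terms in both arms, so any fair comparison of harms must rest on it. Two features weaken it.

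First, five of its six laboratory events depend on someone deciding that a value is abnormal enough to record. That person knows the arm and works from a list headed as expected events or reactions. Nothing says the abnormality must have arisen after randomisation. The calcium exclusion is "Symptomatic hypocalcaemia (Ionised calcium <1.05 mmol/L"), so a patient with a value below that limit and no symptoms can enter, and the protocol does not say whether the pre-existing value then counts. If one arm also has more blood gases, brief abnormalities are more likely to be seen there.

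Second, two effects that the protocol raises are left to the unlisted stream, where the chance of being reported depends on whether a dose was given.

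The primary outcome, 90-day mortality, is untouched. At stake are the harms table and the safety information that the Data Monitoring and Ethics Committee receives. Events never recorded for control patients cannot be recovered by a later analysis plan.

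**Working it through.** The plan gives no figure of its own on this point. The check is a reading of the reporting rules by arm, followed by a bounding calculation for unequal sampling.

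**Reporting route by arm.** This combines section 4.8.1 (a reaction must be related to an administered dose), section 4.8.2.2 (anything at least possibly related is a reaction), section 4.8.3, and the note to Figure 1 (report if association is uncertain).

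| Event | After a bicarbonate dose | Control patient, no dose |
|---|---|---|
| On the Appendix 2 list | Recorded | Recorded, same window |
| Unlisted, non-serious | Recorded if judged at least possibly related | Medical notes only |
| Unlisted, serious, of a kind to be expected in critical illness | Reported if judged at least possibly related | Not reported |
| Unlisted, serious, not of that kind | Reported | Reported |

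The middle two rows differ between the arms. Cardiac suppression and raised PaCO2 can fall in either.

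**How many extra gases.** The Summary says "Starting dose is 50 ml administered over 30-60 minutes", and section 4.5.1.2 caps the total at 500 ml per 24 hours. If every repeat is 50 ml, 500 / 50 = 10 infusions, hence up to 10 post-infusion gases a day. That is an extreme. An infusion of 0.5–1 h plus a gas 1–2 h later is a cycle of 1.5–3 h, so ten consecutive cycles take 15–30 h. The protocol does not say whether these gases add to routine ones or replace some of them.

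**What unequal sampling could do.** Assumptions, none from the documents: the same true incidence in both arms (10%), an abnormality lasting D hours, and g evenly spaced gases a day. Then

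P(detected) = min(1, D × g / 24), and observed rate = 10% × P(detected).

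- D = 2, 6 routine gases in both arms, 3 extra with bicarbonate: control 2 × 6/24 = 0.50, giving 5.0%; intervention 2 × 9/24 = 0.75, giving 7.5%. Spurious risk ratio 1.5. With 2250 / 2 = 1125 per arm, the chance of p < 0.05 is about 69%.
- Same, 10 extra: intervention 2 × 16/24 exceeds 1, so 10.0%. Risk ratio 2.0.
- D = 2, 12 routine gases: 2 × 12/24 = 1 in both arms. Risk ratio 1.0.
- D = 4, 6 routine gases: 4 × 6/24 = 1 in both arms. Risk ratio 1.0.
- D = 1, 4 routine, 10 extra: 4/24 = 0.167 against 14/24 = 0.583. Risk ratio 3.5.

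Over D of 1–4 h, 4–24 routine gases and 1–10 extra, the ratio runs from 1.0 to 3.5. The documents do not say where in that range the trial lies.

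**The case against.** A reader might infer that the safety comparison is biased by design, that the reaction window is an unequal observation window, or that control patients will have no count at all for cardiac or carbon dioxide effects. The protocol does not support any of these.

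- A reaction is defined in section 4.8.1 as related to an administered dose. A window opening at the first dose follows from that definition, and would also cover a control patient who was given bicarbonate.
- Listed events share one window in all randomised patients. Unlisted, unexpected serious events are reportable in either arm unless judged a complication to be expected. Respiratory and advanced cardiovascular support are secondary outcomes taken from routine data in both arms, so severe consequences have an arm-neutral measure.
- Missing cut-offs apply to both arms. They become differential only through open judgement or unequal sampling. Calcium values already low at entry should be balanced by randomisation.
- Routine gases may be frequent enough to make the sampling effect nil. Sodium or calcium disturbances may also persist across several samples, which shrinks it further. The intervention flow diagram is not shown in the text at hand and may bear on monitoring.
- The protocol states no between-arm safety test, and numeric definitions may sit in the case report form (CRF) or the analysis plan.

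Most of this stands, and it removes the strong claims. It leaves two things. Appendix 2 defines one laboratory event and leaves five to open judgement, although limits for three of them already exist in the eligibility criteria. And the two unlisted effects pass through a reporting rule that gives different results by arm. An analysis plan can repair neither if the events were not captured: the trial-specific items in section 4.9.3 include adverse event reporting but no serial laboratory results.

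**Conclusion.** The point holds as a risk of detection bias in the listed laboratory events, of unknown size and possibly none, together with reported counts of cardiac suppression and raised PaCO2 that cannot be compared between arms when the event is non-serious or judged an expected complication. The 1.0 to 3.5 range rests wholly on assumed sampling rates and durations. It shows that a material distortion is possible, not that one will occur. The reaction window quoted from section 4.8.3 is not itself a fault. The defect lies in the definitions and coverage of Appendix 2, and it is worth correcting because the correction is cheap and the lost data cannot be recovered.

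**What to change.** In Appendix 2 and the CRF:

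1. Give each listed laboratory event a numeric cut-off applied identically in both arms. Reuse the protocol's own limits where they exist: sodium above 150, potassium below 3.0 and ionised calcium below 1.05 mmol/L, with pH 7.55 or above already set. The sponsor must choose limits for glucose and osmolarity, for which the protocol has none. (The sodium limit is labelled hypernatraemia in the Summary but hyponatraemia in section 4.3.2; these must be reconciled.)
2. Count only values that newly cross the cut-off after randomisation.
3. Add raised PaCO2, for example 6.5 kPa or above (the complement of the entry limit), and an operationally defined cardiac suppression event to the list recorded for all randomised patients.
4. State that other unlisted reactions are descriptive only and not for comparison between arms.
5. Note the unequal blood-gas schedule when laboratory events are interpreted. Cut-offs remove discretion in labelling but not the difference in sampling, and this applies to the PaCO2 event too.

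The cost is slightly more CRF recording. Abnormalities milder than the cut-offs will not be counted; the potassium limit, for instance, is the one the protocol calls severe. Treatment, blood sampling and individual safety reporting are unchanged.
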